8.1 RECIST Criteria for response

The Response Evaluation Criteria in Solid Tumors (RECIST 1.0) guidelines will be employed in this study. For the purposes of this study, target lesions are defined as metastatic lesions that are bidirectionally measurable with one diameter measuring at least 2 cm (or 1 cm with spiral CT scan). All lesions up to a maximum of 10 lesions representative of all involved organs should be identified as target lesions and will be recorded and measured at baseline. Target lesions should be selected on the basis of their size (lesions with the longest diameter) and their suitability for accurate repetitive measurements (either by imaging techniques or clinically). A sum of the longest diameter (LD) for all target lesions will be calculated and reported as the baseline sum LD. The baseline sum LD will be used as reference to further characterize the objective tumor response of the measurable dimension of the disease.

Measurable disease: lesions that can be accurately measured in at least one dimension (longest diameter to be recorded) as ≥ 2 cm with conventional techniques or as ≥ 1 cm with spiral CT scan.

Non-measurable disease: all other lesions, including small lesions (longest diameter < 2 cm with conventional techniques or < 1 cm with spiral CT scan).

Complete response (CR): complete disappearance of all target lesions, confirmed by repeat assessments at no less than 4 weeks after the criteria for response are first met.

Partial response (PR): at least a 30% decrease in the sum of the longest diameter of target lesions, taking as reference the baseline sum longest diameter. This must be confirmed by repeat assessment at no less than 4 weeks after the criteria for response are first met.

Progressive disease (PD): at least a 20% increase in the sum of the longest diameter of target lesions, taking as reference the smallest sum longest diameter recorded since the treatment started or the appearance of one or more new lesions.

Stable Disease (SD): neither sufficient decrease to qualify for partial response nor sufficient increase to qualify for progressive disease, taking as reference the smallest sum longest diameter since the treatment started.

Non-target Lesions: all other lesions (or sites of disease) not included in the “target disease” definition should be identified as non-target lesions and should also be recorded at baseline. Measurements are not required and these lesions should be followed as “present” or “absent”.

Complete Response: Disappearance of all non-target lesions.

Non-complete response/Non-progression: Persistence of one or more non-target lesions.

Progression: Appearance of one or more new lesions. Unequivocal progression of existing non-target lesions.

Cytology and Histology: if the measurable disease is restricted to a solitary lesion, its neoplastic nature should ideally be confirmed by cytology or histology. These techniques can be used to differentiate between PR and CR in rare cases.

The cytological confirmation of the neoplastic origin of any effusion that appears or worsens during treatment when the measurable tumor has met criteria for response or stable disease is mandatory to differentiate between response, stable disease, and progressive disease

Evaluation of Best Overall Response: the best overall response recorded from the start of the treatment until disease progression/recurrence (taking as reference for progressive disease the smallest measurements recorded since the treatment started). In general, the patient’s best response assignment will depend on the achievement of both measurement and confirmation criteria.

Table 8.1 Evaluation of best overall response

Target Lesions	Non-target Lesions	New Lesions	Overall Response
----------------	--------------------	-------------	------------------

CR	CR	No	CR
CR	Non-CR/Non-PD	No	PR
PR	Non-PD	No	PR
SD	Non-PD	No	SD
PD	Any	Yes or No	PD
Any	PD	Yes or No	PD
Any	Any	Yes	PD

Note:

Patients with a global deterioration of health status requiring discontinuation of treatment without objective evidence of disease progression at that time should be reported as “symptomatic deterioration”. Every effort should be made to document the objective progression even after discontinuation of treatment.

In some circumstances it may be difficult to distinguish residual disease from normal tissue. When the evaluation of complete response depends upon this determination, it is recommended that the residual lesion be investigated (fine needle aspirate/biopsy) before confirming the complete response status.

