The primary purpose of the study is to investigate the progression-free survival associated with pasireotide LAR in treatment-naïve patients with metastatic carcinoid and pancreatic neuroendocrine tumors.

Secondary objectives are to assess the overall survival (OS) associated with pasireotide LAR, overall radiographic response rate (ORR), adverse events (AEs), changes in tumor markers and changes in quality of life (QOL).

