4.2 Follow-up

All patients will be followed for adverse events and serious adverse events for 28 days following the last dose of pasireotide, or until resolution or stabilization of the event, whichever comes first.

5 Population

The study population will consist of patients with advanced (metastatic or unresectable) well and moderately differentiated neuroendocrine tumors of the gastrointestinal tract and lungs (carcinoid tumors) and pancreatic neuroendocrine tumors.

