5.1.1 Inclusion criteria

1. Locally unresectable or metastatic carcinoid or pancreatic neuroendocrine tumors.
2. Tumors must be considered well or moderately differentiated (or low to intermediate grade). Patients with poorly differentiated neuroendocrine carcinomas or small cell carcinomas are excluded from the study.
3. No prior systemic antineoplastic neuroendocrine tumor treatment (including prior somatostatin analogs). However patients who have received a short course of SQ octreotide (<10 days) in the past are eligible if > 1 week has elapsed from their last octreotide injection.
4. Age \geq 18 years.
5. Minimum of four weeks since any major surgery.
6. Measureable disease by RECIST.
7. ECOG performance status \leq 1
8. Life expectancy 12 weeks or more.
9. Adequate bone marrow function as shown by: ANC \geq $1.0 \times 10^9/L$, Platelets \geq $75 \times 10^9/L$, Hgb $>$ 8 g/dL.
10. Adequate liver function as shown by: serum bilirubin \leq 2.0 x upper limit of normal (ULN), and serum transaminases activity \leq 2 x ULN, with the exception of serum transaminases ($<$ 3 x ULN) if the patient has liver metastases.
11. Adequate renal function as shown by serum creatinine \leq 2.0 x ULN.

12. Fasting serum cholesterol ≤ 300 mg/dL OR ≤ 7.75 mmol/L AND fasting triglycerides ≤ 2.5 x ULN. NOTE: In case one or both of these thresholds are exceeded, the patient can only be included after initiation of appropriate lipid lowering medication.
13. Women of childbearing potential must have a negative serum pregnancy test within 14 days of the administration of the first study treatment. Women must not be lactating. Both men and women of childbearing potential must be advised of the importance of using effective birth control measures during the course of the study.
14. Signed informed consent to participate in the study must be obtained from patients after they have been fully informed of the nature and potential risks by the investigator (or his/her designee) with the aid of written information.

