The primary efficacy endpoint is progression-free survival, defined as the time from the date of first study treatment to the date of the first documented disease progression (by RECIST criteria) or death due to any cause. If a patient has not progressed or died at the date of the analysis cut-off or when he/she receives any further anti-cancer therapy, PFS is censored at the time of the last tumor assessment before the cut-off or the anti-cancer therapy date.

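### Section 8.1 confines target lesions to metastases, so an eligible patient with only locally unresectable disease has no target lesion by which growth can be scored

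*Combined protocol and SAP*

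**What the plan says.** **Target lesions.** Section 8.1 rules, for this study, that "target lesions are defined as metastatic lesions that are bidirectionally measurable with one diameter measuring at least 2 cm", or 1 cm with spiral CT.

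**Measurable disease.** The same section defines this as "lesions that can be accurately measured in at least one dimension", with the same size thresholds and no condition on site. Only longest diameters enter the sum.

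**Everything else.** Section 8.1 makes any lesion outside the target definition non-target. Such lesions need no measurement and are tracked only by presence or absence.

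**Eligibility.** Inclusion criterion 1 in section 5.1.1 reads "Locally unresectable or metastatic carcinoid or pancreatic neuroendocrine tumors", and criterion 6 reads "Measureable disease by RECIST". Section 5 (Population) describes "patients with advanced (metastatic or unresectable) well and moderately differentiated neuroendocrine tumors", and Subset 2 in section 11.3 again allows for unresectable disease. Section 2 (Study objectives) is narrower and speaks of "treatment-naïve patients with metastatic carcinoid and pancreatic neuroendocrine tumors".

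**Primary endpoint.** Under section 8, progression-free survival (PFS) runs from first treatment to "the date of the first documented disease progression (by RECIST criteria) or death due to any cause".

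**The concern.** The people who may enter and the lesions that may be measured are defined differently. A patient with an unresectable primary and no metastases is plainly admitted, because the population is described three times as including unresectable disease. Yet that patient's only measurable lesion falls outside the target definition and so goes unmeasured.

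The primary endpoint is at stake. PFS and its 12-month rate rest on RECIST progression, in an open-label, multi-institutional trial with no control arm. If growth cannot be scored by a size rule in some patients, their progression depends on a reader's judgement of non-target disease. Different sites may also choose different lesions for similar patients.

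**Working it through.** The plan gives no figure on this point, so the check is mainly a comparison of its rules. The nearest figure is the power in section 11.2, which is checked in step 5.

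**1. Can such a patient enter?** Yes. Criterion 1 joins locally unresectable and metastatic disease with *or*. Criterion 6 asks only for measurable disease, and the definition in section 8.1 is met by one accurately measured dimension at any site.

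**2. What do the rules give for a patient whose only measurable disease is an unresectable primary or locoregional mass?**

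| Rule | What it needs | Result |
|---|---|---|
| Progression by growth (8.1) | 20% rise over the smallest target sum | No sum, cannot be applied |
| Partial response (8.1) | 30% fall from the baseline sum | Cannot be applied |
| Stable disease (8.1) | A sum between those limits | Cannot be applied |
| Table 8.1, not progressing | Target status CR, PR or SD | No row fits |
| Table 8.1, progressing | Non-target progression or a new lesion, any target status | Applies |
| Table 8.4, all five censored rows | Last imaging of measured lesions | No measured lesion, so no date |
| Death (8, Table 8.4) | Date of death | Applies, except in the row censoring death after more than two missed visits |

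Three routes to an event remain: a new lesion, unequivocal non-target progression, and death. The size-based route is lost.

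**3. Which way does this push the endpoint?** In the patient above, a 20% size threshold is replaced by a judgement on an unmeasured lesion, so progression by growth may be detected later.

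In a patient with metastases and a primary left in place, the direction depends on which lesion grows. As an illustration with assumed sizes, take a 5 cm primary and metastases summing to 5 cm:
- Metastases grow to 6 cm, primary stable. With the primary: (5 + 6)/(5 + 5) = 1.10, +10%, not progression. Without it: 6/5 = 1.20, +20%, progression. Excluding the primary brings the event **earlier**.
- Primary grows by 2 cm (20% of the 10 cm total), metastases stable. With the primary: (7 + 5)/(5 + 5) = 1.20, progression. Without it: 5/5 = 1.00, no change. Excluding the primary makes the event **later**, unless it is called on non-target grounds.

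**4. What does the two-direction requirement add?** The size condition applies to one diameter only and matches the threshold for measurable disease. A second measurable direction is required but never used, because the sum takes longest diameters. On its wording it could exclude a lesion measurable in one direction only. The documents give no sign that such patients are expected.

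**5. Are the design figures affected?** Section 11.2 gives null 19%, alternative 40%, one-sided alpha 10% and 90% power at n = 30. The normal approximation gives

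n = [(1.2816 × √(0.19 × 0.81) + 1.2816 × √(0.40 × 0.60)) / 0.21]² = 28.98,

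that is 29, with power 90.7% at n = 30. The plan's figure reproduces. No input to it depends on the target-lesion definition, so nothing changes after the correction.

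**The case against.** **Section 8.1 can be read more generously.** It adopts RECIST 1.0, and the sentence after the disputed one asks for up to ten target lesions covering every involved organ. A site could include a measurable primary on that basis. This softens the conflict but does not remove it. The restriction is stated as a rule for this study, and neither sentence makes an exception to it. At best two readings are open to different sites.

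**A censoring date exists elsewhere.** Sections 8 and 8.3 censor at the last tumor assessment, which such a patient would have. That is fair, and a date could be recovered from there. But Table 8.4 is the place that instructs how to classify each situation, and all its censored rows point to measured lesions.

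**A stricter target definition is not in itself a contradiction.** This also stands. Target lesions may properly be a subset of measurable ones, so the two-direction wording is untidy rather than harmful. The difficulty is that the metastatic restriction can leave an eligible patient with an empty subset and no stated way to score it.

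**Few patients may be concerned.** Section 2 names metastatic disease only, so entrants without metastases may be rare. This bears on the size of the problem, not on whether the rules conflict.

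**Stronger readings that the documents do not support.** A reader might infer that PFS cannot be determined at all in these patients. It can, through the three routes that remain. A reader might also infer that the definition always delays progression. The first example in step 3 shows the opposite.

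**Conclusion.** The point holds as an internal contradiction in how the primary endpoint is measured. As written, an eligible patient with only an unresectable primary or locoregional mass has no target lesion. Growth, partial response and stable disease cannot be scored by the stated rules, and Tables 8.1 and 8.4 do not cover the patient while not progressing.

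The size cannot be stated, because the documents do not say how many patients without metastases are expected. In a simple proportion, one patient carries 1/35 = 2.9 percentage points (35 planned in section 11.1) or 1/30 = 3.3 (the 30 used in section 11.2). That is the weight of a single patient, not an estimate of bias.

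A reader might go further and attach an error rate. At n = 35 and a true rate of 19%, 10 or more successes has probability 11.3%, and 11 or more has 5.5%. That gap is the coarseness of a binomial count and would follow from any single misclassified patient. A cutoff of 10 would also exceed the plan's 10% alpha. No alpha or power figure follows from this defect.

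The conclusion rests on a literal reading of the target-lesion sentence and on criterion 1 meaning what it says.

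**What to change.** Replace the target-lesion sentence in section 8.1 with wording such as: *Target lesions are measurable lesions (at least one dimension, 2 cm or more by conventional technique or 1 cm or more by spiral CT) at primary, locoregional or metastatic sites.* Deleting the metastatic restriction is the substantive change. Dropping the two-direction requirement is an editorial alignment with the sum of longest diameters.

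Tables 8.1 and 8.4 then work for these patients without change. Narrowing eligibility instead would mean changing sections 5, 5.1.1 and 11.3.

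The cost is one sentence and no new procedure. There is one small downside. If patients already have baseline sums, those with a measurable primary may need target lesions reselected and remeasured from existing scans. That assumes the baseline scan covered the primary. Footnote h to Table 7-3 asks only for known metastatic sites, so coverage should be checked.

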8.2 Guidelines for Evaluation of Measurable Disease

Clinical Lesions: Clinical lesions will only be considered measurable when they are superficial (e.g. skin nodules, palpable lymph nodes). For the case of skin lesions, documentation by color photography including a ruler to estimate the size of the lesion is recommended.

CT scan: Conventional CT scan should be performed with cuts of 10mm or less in slice thickness contiguously. Spiral CT scan should be performed using a 5mm contiguous reconstruction algorithm.

8.3 Confirmation Measurement/Duration of Response

Confirmation: To be assigned a status of PR or CR, changes in tumor measurements must be confirmed by repeat studies that should be performed no less than 4 weeks after the criteria for response are first met. In the case of SD, follow-up measurements must have met the SD criteria at least once after study entry at a minimum interval of 6 weeks.

Duration of Overall Response: The duration of overall response is measured from the time measurement criteria are met for CR/PR (whichever is first recorded) until the first date that recurrent or progressive disease is objectively documented (taking as reference for progressive disease the smallest measurements recorded since the treatment started).

The duration of overall complete response is measured from the time measurement criteria are first met for CR until the first date that recurrent disease is objectively documented.

Duration of Stable Disease: Stable disease is measured from the start of the treatment until the criteria for progression are met, taking as reference the smallest measurements recorded since the treatment started.

Progression Free Survival (PFS): PFS is defined as the time from the date of first study treatment to the date of the first documented disease progression or death due to any cause. If a patient has not progressed or died at the date of the analysis cut-off or when he/she receives any further anti-cancer therapy, PFS is censored at the time of the last tumor assessment before the cut-off or the anti-cancer therapy date.

8.4 PFS and Censoring

Since disease progression is assessed periodically, the true date of disease progression is known only to occur at a time point after the last radiological assessment of stable disease (or better) and prior to the date of the scan detecting progression. Table 8.4 provides instructions on classification of the primary endpoint (PFS) depending on various clinical scenarios.

Table 8.4: Classification of Primary Outcome

Situation	Outcome	Date of Progression or Censoring
Progression documented between scheduled visits	Progressed	Earliest of: Date of radiologic assessment showing new lesion (if progression is based on new lesion); or Date of last radiologic assessment of measured lesions (if progression is based on increase in sum of measured lesions)
No progression	Censored	Date of last radiologic assessment of measured lesions
Treatment discontinuation for undocumented progression	Censored	Date of last radiologic assessment of measured lesions
Treatment discontinuation for	Censored	Date of last radiologic assessment of

toxicity or other reason		measured lesions
New anticancer treatment started	Censored	Date of last radiologic assessment of measured lesions
Death before first progressive disease assessment	Progressed	Date of death
Death between adequate assessment visits	Progressed	Date of death
Death after one to two missed visits	Progressed	Date of death
Progression after one to two missed visits	Progressed	Earliest of: Date of radiologic assessment showing new lesion (if progression is based on new lesion); or Date of last radiologic assessment of measured lesions (if progression is based on increase in sum of measured lesions)
Death or progression after more than two missed visits	Censored	Date of last radiologic assessment of measured lesions

9 Safety monitoring

Safety assessments will consist of monitoring and recording all adverse events and serious adverse events, the regular monitoring of hematology and blood chemistry parameters and regular physical examinations. Adverse events will be evaluated continuously throughout the study. Safety and tolerability will be assessed according to the NIH/NCI Common Terminology Criteria for Adverse Events version 4.0 (CTCAE v4.0) that is available at:

<http://evs.nci.nih.gov/ftp1/CTCAE/About.html>

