6.4 End of treatment

Patients may voluntarily withdraw from the study or be dropped from it at the discretion of the investigator at any time. Patients will be withdrawn from the study if any of the following occur:

- Disease progression
- Death
- Withdrawal of consent
- Delay of treatment >21 days.
- Uncontrolled diabetes mellitus (DM)
- Pregnancy
- Adverse event(s) \geq grade 3 despite dose reduction
- QTc prolongation (see section 6.3.2)

7 Visit schedule and assessments

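### Table 8.4 censors patients who discontinue treatment and gives no rule for a later progression or death, which Section 8 counts as a PFS event

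*Combined protocol and SAP*

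**What the plan says.** Section 8, repeated in Section 8.3, runs PFS from first study treatment to "the date of the first documented disease progression or death due to any cause". Censoring is tied to two situations only: "If a patient has not progressed or died at the date of the analysis cut-off or when he/she receives any further anti-cancer therapy". In both, the censoring date is the last tumour assessment beforehand. Neither section mentions stopping treatment or missing visits.

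Section 8.4 presents Table 8.4 as the instructions for classifying the primary endpoint. The rows that matter here are:

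- "Treatment discontinuation for undocumented progression", and a second row for stopping because of toxicity or any other cause: both censored at the last radiologic assessment.
- "Death before first progressive disease assessment" and "Death between adequate assessment visits": both counted as progressed on the date of death.
- "Death or progression after more than two missed visits": censored at the last radiologic assessment.

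The table has no order of precedence and no statement that it overrides or refines Section 8. Section 8 does not refer to the table. The note to Table 8.1 says of patients who stop for symptomatic deterioration: "Every effort should be made to document the objective progression even after discontinuation of treatment".

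**The concern.** One patient can be an event under the definition and a censored observation under the table that is meant to apply it. The patient in question is not exotic: someone who leaves treatment without radiologic progression, takes no new therapy, and later progresses or dies. Section 6.4 lists several ways off treatment other than progression.

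The trial is open-label and single-arm, with about 30 patients tested against a fixed 12-month rate of 19%. If precedence is not written down, the classification could be settled after outcomes are known, and a few patients can move the estimate. Deaths soon after a stop are also likely to be related to the disease, so censoring them would not be neutral.

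**Working it through.** **1. The plan's own figure.** Section 11.2 gives n=30, one-sided alpha 10%, 19% against 40%, and 90% power. Medians of 5 and 9 months give 0.5^(12/5) = 0.189 and 0.5^(12/9) = 0.397. The documents state no cut-off. Assuming rejection at 9 or more of 30, P(X≥9 | 0.19) = 10.0% and P(X≥9 | 0.40) = 90.6%. The stated power is reproduced.

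**2. The rules side by side.** No new therapy is taken in any of these cases.

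| Patient | Section 8 | Table 8.4 |
|---|---|---|
| Stops for toxicity, stable scan at week 14, no later event | Censored, week 14 | Censored, week 14 |
| Same patient, dies at week 22 | Event, week 22 | Toxicity row: censored, week 14 |
| Last scan week 12; scans at weeks 24, 36 and 48 missed; dies at week 50 | Event, week 50 | Last row, counting scans: censored, week 12 |

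The first line agrees, so the discontinuation rows are harmless when nothing follows. The second is the main conflict, and it involves no missed visit. The third is the secondary one.

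**3. How often the last row can apply.** Sections 6.3 and 6.4 take a patient off for "Delay of treatment >21 days". If a visit is a 28-day cycle visit, three missed visits span 3 × 28 = 84 days, so such a patient will usually have met a discontinuation row already. If a visit is a scan, the patient must miss three in a row, 3 × 12 = 36 weeks, while still on study. After a stop, Section 7.3 lists one end-of-treatment scan and Section 4.2 lists 28 days of adverse-event follow-up. No later tumour visit is scheduled that could be missed.

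**4. One patient, Kaplan-Meier.** Start from 8 of 30 progression-free at month 12, with the 22 failures at exponential quantiles: 8/30 = 26.7%, one-sided 90% lower bound 17.0%.

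- Week-22 death censored at week 14 (9 failures before it): 21/30 × 8/20 = 28.0%, bound 17.9%.
- Week-50 death censored at week 12 (8 failures before it): 22/30 × 8/21 = 27.9%, bound 17.9%.
- Death at week 62, last scan week 24, censored at week 24 (14 failures before it; the patient was otherwise among the 8): 16/30 × 7/15 = 24.9%, bound 15.3%.

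No bound crosses 19%, and the direction differs.

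**5. Type I error by simulation.** Assumptions: n=30, exponential PFS with a true 12-month rate of 19%, follow-up capped at 24 months. A share of failures are deaths within 3 months of a stop, censored at the end-of-treatment scan. Rejection means a one-sided 90% lower bound above 19% (log-log for Kaplan-Meier), or 9 or more of 30 for the binomial count.

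| Share of failures censored | 0% | 5% | 10% | 20% |
|---|---|---|---|---|
| Kaplan-Meier | 10.0% | 12.2% | 16.5% | 27.8% |
| Exponential bound | about 7.5% | about 11% | about 16% | about 31% |
| Binomial, censored before month 12 = failure | 10.0% | 9.5% | 9.2% | 8.3% |

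For the last row alone under Kaplan-Meier, with 0/5/10/20% of eligible failures censored, type I error is 10.0/8.8/7.7/6.7% if visits are scans and 10.0/10.6/11.8/16.1% if they are 28-day visits.

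**The case against.** **A general definition followed by a specific table is a normal layout, and censoring after several missed assessments is a common convention.** Both are true, and the convention is not the fault. But a table that reverses the event status of a death needs to say that it does so, and this one does not.

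**The table may not contradict itself.** The row "Death before first progressive disease assessment" can mean death before the first assessment for progression. The week-22 patient has already been scanned, so on that reading the row does not apply. With no later visit scheduled, "Death between adequate assessment visits" is doubtful too. This stands: the overlap inside the table exists on one reading only. The conflict with Section 8 remains on either reading.

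**A sensible reader would let the more specific event prevail.** The general row for patients without progression literally overlaps every death row, which supports this. It does not decide whether stopping for toxicity or dying is the more specific event, and the last row shows that death does not always prevail.

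**The inflated error rates need an estimator that the plan does not name.** This is right for Kaplan-Meier. Section 11.2 names binomial theory for the sample size and, if a test of exponentiality gives p above 0.20, an exponential lower bound. That bound moves the same way as Kaplan-Meier, while the binomial count moves the other way. Nothing in the documents supports a particular share such as 20%.

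**Conclusion.** Table 8.4 is wrong as written for patients who discontinue and later progress or die without new therapy: Section 8 makes them events, and the discontinuation rows make them censored. The last row is a real but secondary mismatch that few patients can reach, and the word visit is undefined.

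The size is illustrative. It rests on assumed shares, exponential PFS, 30 patients and a chosen estimator. Censoring deaths soon after a stop raises type I error under Kaplan-Meier or the exponential bound, and lowers it when censored patients count as binomial failures. The plan does not say how patients censored before month 12 enter the test.

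Two stronger inferences are tempting and not supported. One is that the missed-visit row is the main fault and favours the drug: with visits read as scans it lowers type I error. The other is that the trial's error rate is near 28%: that figure needs one failure in five to be a death shortly after a stop, plus an analysis based on censoring. The documents establish an unreconciled rule for the primary endpoint, not a bias of known size. It should be corrected before the data are analysed.

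**What to change.** 1. State that the Section 8 definition governs, and cross-reference Table 8.4 to it.
2. Limit the discontinuation rows to patients with no later documented progression or death before new anti-cancer therapy. Count a death before new therapy as an event on the date of death.
3. Define a visit in Table 8.4 as a scheduled tumour assessment.
4. For progression first found after more than two missed tumour assessments, keep the table's censoring in the primary analysis as a stated exception to Section 8. Add a sensitivity analysis that counts it as an event at the first missed assessment.

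Item 4 avoids a remedy that could do more harm. If 5/10/20% of patients had progression dated 36 weeks late, counting it on the detection date would give a Kaplan-Meier type I error of 16.3/24.2/43.2%, against 12.3/16.4/27.7% with censoring at the last scan.

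The cost is wording, with no added scans. Deaths and new therapies after treatment stops must be recorded. The overall survival endpoint in Section 3.2 already needs the deaths, but the follow-up sections set no schedule for collecting either. The PFS estimate may change in either direction.
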